Title: Role of blood management in optimizing perioperative outcomes in patients with secondary anemia undergoing hysterectomy for abnormal uterine bleeding: A Proposed Randomized Control Trial

Principal Investigators: [name] MD (Head, Section of Benign Gynecology)

[name] MD (PGY-2, Ob/Gyn Residency Program)

Co-Investigators: [name] MD (Benign Gyn Surgery/MIGS staff)

[name] (Benign Gyn Surgery/MIGS staff) [name] MD (PGY-5, Fellowship in MIGS)

[name] MS (Statistician)

[name] DO (Director, Benign Gyn Surgery) [name] (PGY-5, Fellowship in MIGS)

I. Background/Introduction:

According to the World Health Organization (WHO), 30.2 % of the world's population of nonpregnant women are anemic (1), with a higher percentage of anemia being encountered in patients seeking surgical management of abnormal uterine bleeding (AUB). Age, gender, socioeconomic factors, nutrition, and certain pathologic states are associated with iron depletion and associated iron deficiency anemia. Uterine fibroid (or leiomyoma) is the most common diagnosis associated with hysterectomy, accounting for approximately 31% of all procedures performed. Abnormal uterine bleeding and endometriosis are the second and third most common diagnoses associated with hysterectomy, explaining 14% and 11%, respectively (2). Based on the diagnoses recorded in the medical record by providers, 48.7% of patients were presumed to have dysfunctional uterine bleeding (DUB) and 9% were presumed to have bleeding secondary to uterine fibroids. In this population of women with AUB, 350 (92.3%) had a hemoglobin concentration recorded. Thirty-five percent were anemic with a hemoglobin of <10 g/dL (3).

In addition to the high incidence of secondary anemia in patients with abnormal uterine bleeding and fibroids, surgeries for abnormal uterine bleeding and fibroids such as hysterectomy and myomectomy can involve a significant blood loss (4,5). The overall rate of postoperative blood transfusion for hysterectomy in the cited study was 13.3% (5). The need for packed red blood cell transfusion is one of the known complications of surgery and is increased in women who are noted to be anemic preoperatively. Blood transfusions are associated with increased adverse surgical outcomes. Higher rates of morbidity and mortality have been reported in patients receiving one unit of packed red blood cells compared with patients who did not undergo transfusion (6). The WHO recommends, in compliance with their guide for optimal clinical use, "that before surgery every reasonable measure should be taken to optimize the patient's own blood volume" (7). Pre-operative hemoglobin less than 10.6 g/dL versus greater than or equal to 13.1 g/dL had five times the odds of transfusion (5).

Anemia is a modifiable risk factor that can be assessed and optimized pre-operatively. Prior studies have evaluated preoperative blood management strategies in oncology patients, patients undergoing general surgery procedures, and orthopedic surgery. A systematic review of the management of perioperative anemia showed varying results in change in hemoglobin levels after blood management intervention, but all studies were able to show a decrease in postoperative blood transfusions (8). A randomized control trial evaluating oral iron supplementation preoperatively in patients undergoing colorectal surgery reported reduced blood transfusion rates in the group receiving this intervention (9). Froessler et al studied perioperative IV iron intervention in patients undergoing major abdominal surgery in a randomized control trial with using blood transfusions as a primary endpoint. They concluded that perioperative IV iron reduced the need for blood transfusion and was also associated with higher postoperative hemoglobin and shorter hospital stay (10). A blood management protocol implemented in the perioperative period also noted a decrease in perioperative blood transfusion and postoperative anemia in the orthopedic population. The interventions used in their blood protocol management included erythropoietin, ferric carboxymaltose, and tranexamic acid (11).

A Blood management protocol was recently developed at the Cleveland Clinic whereby either confirmed or suspected anemic patients with abnormal uterine bleeding scheduled for surgical management are referred to Blood Management for assessment of laboratory studies (CBC, Ferritin, iron, TIBC, %Sat) and a care plan is development. Several factors are considered in designing a treatment plan including current blood loss, anemia symptoms, scheduled or upcoming procedures, and others. Treatment plans may include observation alone or oral iron versus intravenous iron. Iron deficiency is calculated using the Ganzoni calculation for patients receiving intravenous iron. Per the Blood Management Protocol: An anemia screening lab panel will be ordered, in combination with a referral to the Blood Management clinic via WHI Blood Management Referral Smartset. This order set will automatically preselect the lab panel — complete blood count (CBC), iron, total iron binding capacity (TIBC) and ferritin — and the referral to the Blood Management clinic. The patient will automatically receive information in the after-visit summary regarding the Blood Management clinic referral. Any correctable causes of anemia will be addressed preoperatively by the Blood Management group. Measures used may include the use of intravenous iron or oral iron. See Algorithm in Table 2.0.

Using Ganzoni Formula Calculator: http://www.al-nasir.com/www/PharmCalc/mob exec calc.php?ID=ganzoni

Clinical data for calculator:

- a) Current hemoglobin
- b) Weight in kg
- c) Target hemoglobin (see table below)

Ganzoni Target Hemoglobin	Female
High Blood Loss* (> 3 gm/dL)	13 gm/dL

Low Blood Loss* (1-2 gm/dL)	12 gm/dL
Non-surgical*	12 gm/dL
Unknown*	12 gm/dL

*High blood loss defined as expected drop in hemoglobin > gm/dL postoperatively i.e. CABG, Valve, AAA, lower extremity joint replacement,multi-level spine w/instrumentation; Low blood loss expected drop hemoglobin 1-2 gm/dL i.e. hysterectomy, simple colectomy, laparoscopic or robotic assisted procedures; Non-surgical is medical iron deficiency treatment; Unknown are default targets.

There is currently limited information regarding the role of blood management in the benign gynecologic population and specifically, in patients who are scheduled to undergo surgery for fibroids and/or abnormal uterine bleeding. A thorough search through PubMed and clinicaltrials.gov did not reveal any studies on this issue. In 2019 at CCF only 2% of gyn patients at Main Campus were referred to blood management, but 12.6% of the main campus gyn population had a Hb of <10.0 g/dL. The overall goal of this study is to evaluate the role of preoperative blood management in optimizing surgical outcomes by reducing the co-morbidities associated with postoperative blood transfusion.

Specific Aims/Objective:

The primary objective of this study is to compare the change in baseline hemoglobin levels in patients in the study (Blood Management Protocol) and control ("usual care")

group who are undergoing hysterectomy for abnormal uterine bleeding. Change in baseline hemoglobin levels is defined as the difference of the hemoglobin level obtained within 72 hours prior to surgery and the hemoglobin level at 4 weeks postoperatively.

Our secondary objectives include 1. To evaluate the perioperative outcomes between the two groups including OR times, EBL, peri-operative transfusion rates, length of hospital stay, complications including intra-operative injuries, postoperative infection rates, readmission, and re-operation; 2. to assess patient satisfaction regarding their experience with the Blood Management protocol and extra outpatient infusion visits required using a patient questionnaire (PATSAT 35, Attached); and 3. to compare the quality of patient health and recovery between the two groups using the RAND-36 (Attached) assessment tool. The REDCap database will include potential identifiers to enable online surveys. The included potential patient identifiers include: date of birth, surgery date, and subject email (they provide for the study.)

Data variables that will be collected in the study are visible in the following table.

Patier	nt Demographics:
•	MRN
•	Age/ Date of Birth
•	BMI

Race • Gravidity/Parity Prior abdominal surgery Prior cesarean section Diabetes Hypertension **Current Smoker** Former Smoker • Menopause status Type of surgery: Hysterectomy or myomectomy Type: Vaginal, laparoscopic, open, laparoscopic assisted vaginal hysterectomy, robotic • Surgery date, discharge date • Surgery date/ Discharge date • Subject email Primary objectives: • Change in hemoglobin levels o Baseline Hemoglobin (pre-op) o Post Op Hemoglobin level Secondary objectives: • Operative time Blood Loss • Perioperative transfusion rate • Length of hospital stay • Intraoperative Complications o Intraoperative injuries o Post-operative infection rates Readmission Reoperation • Patient Satisfaction • Quality of Health and Recovery • Number of infusions received • Days on PO iron therapy

Table 1.0 -- Data Collection Variables

We anticipate that patients undergoing blood management protocol will have a faster return to normal recovery and better quality of life scores during recovery using the RAND-36 assessment questionnaire compared to patients undergoing usual care. We also plan to evaluate additional cost of blood management treatments for oral iron, IV iron, and blood transfusion in regards to feasibility, and from a health care utilization standpoint.

Methods and Study Design:

This will be a prospective randomized control trial conducted in a single large-referral center where anemic patients undergoing hysterectomy for fibroids or abnormal uterine bleeding will be recruited and randomized to undergo Blood Management protocol or usual care.

Inclusion criteria are anemic patients (defined as Hgb ≤ 11g/dL within 30 days of initial MIGS consult visit), greater than 18 years of age, with abnormal uterine bleeding, or fibroids undergoing hysterectomy by laparoscopic, robotic, vaginal or open routes. Exclusion criteria are malignancy, pregnancy, sickle cell anemia or other blood dyscrasias, women who received blood transfusions in 30 days prior to surgery, women receiving EPO therapy, women who have undergone gastric bypass surgery, and women on therapeutic/full anticoagulation. Patients undergoing hysteroscopic myomectomy alone without will not be included in the study.

Women meeting the above inclusion criteria who are undergoing elective surgery (hysterectomy) at the Cleveland Clinic Main Campus will be randomly allocated to receive presurgical optimization blood management referral versus usual care - defined as expectant management with no therapy, or PO iron therapy at the primary surgeon's discretion. Randomization following a computer generated number sequence and allocation will occur in person. Patients will be screened from multiple minimally invasive gynecologic providers with high volume surgical practices at a large teaching institution, and consented on their initial preoperative visit. (These MIGS surgeons are [name], [name], [name], [name].) Patients will be randomized to receiving a blood management referral or usual care. Patients will be randomized with permuted block randomization with block size 2 and stratified on care providers. Blood management work up protocol is visible in Table 1. Patients receiving usual care will receive anemia management provided by the primary physician that may include no treatment, continued observation, or oral iron recommendations in the pre-operative time.

The intervention will include pre-surgical optimization blood management referral based on preoperative Hb levels ≤11.0. Currently it is not standard of care at the Cleveland Clinic to send all patients with Hb ≤11.0 due to secondary anemia to blood management. It is done currently at the provider/surgeons preference alone and not through a research protocol or guidelines. At the initial consultation visit a CBC will be drawn, patients will be given a consent form for the study and asked to review it. If a Hb ≤11.0 within 30 days of consultation visit is documented in EPIC, they will be consented and randomized at the consultation visit. All patients after initial consultation visit will be immediately sent to the lab for blood draw if they have not had Hb drawn within 30 days. Lab draw includes: CBC + differential, iron studies: iron, TIBC, ferritin, optional B12. If the initial consult visit occurs at Fairview or Hillcrest Hospital, the patient's follow up preoperative visit will be scheduled at the main campus where consent will be obtained. The blood management team then will receive the referral from primary surgeon's office via EPIC inbasket. Blood management coordinator will assess patient, arrange treatment, and orders will be cosigned by surgeon/referring provider. Blood management may further assess for symptoms of PICA, restless legs, and cold intolerance as symptomatic indicators of anemia. The Rand 36 study will be administered at either the consultation or the pre-operative visit. The PATSAT 35 will be administered at the postoperative visit only. Postoperative Hb levels will be collected by a CBC at the post-operative visit. All postoperative visits will be scheduled at the main campus. All surveys and consents will be obtained at visits that occur at the main campus.

[figure not shown]

Table 2: Blood Management Preoperative Iron Deficiency Algorithm

Blood loss intraoperatively will be measured as accurately as possible with suction device recording and quantitative blood loss and tapes/packs by weighing instead of only visual assessment.

[figure not shown]

Image: 1.0 -- Patient Flow Sheet

Justification for Sample Size:

Power Calculation:

Sample size was calculated to have 80% power to detect a difference between groups using a T-test at a significance level of 0.05. We assume that patients at 4 weeks will have a standard deviation in hemoglobin values of 1.2 g/dL (8) to detect a 1 g/dL difference between groups, we

will need 48 patients total (24 per group) if the groups are of equal size. Assuming a 20% dropout rate, 60 patients total (30 per group) will be the target enrollment.

Cost and Payments to Subjects

The patients will have no additional costs due to participating in the study beyond the usual insurance copays and standard costs for appointments.

Quality Control Procedure:

Information will be provided to all department members involved in administration of the study. Follow up, data entry, and patient follow up will be closely followed by the research team (resident, fellow, staff physicians, MIGS NP's, Lead research nurse)

Process of Consent

Patients would be consented for participation in the study at their primary surgeon's office when shared decision making for proceeding with surgery is performed. Patients will receive no difference in care based on their participation in the study apart from the study protocol

Risks and Discomfort of the Project

The study has been designed to minimize as much risk as possible, and participants will be subjected to no more than minimal or standard risk for undergoing the intervention. Breach of confidentiality is a small risk. Physical risk are rare and unanticipated but would be limited to transfusion reaction to the IV iron therapy. There are no psychological risks for patients who participate in this study. Participants can also benefit from their participation in this study due to their altruistic motivation for partaking in research study they have contributed to scientific advancement.

Analysis plan

Approximately normally-distributed continuous measures will be summarized using means and standard deviations and will be compared using two-sample t-tests. Continuous measures that show departure from normality and ordinal measures will be summarized using medians and quartiles and will be compared using Wilcoxon rank sum tests. Categorical factors will be summarized using frequencies and percentages and will be compared using Pearson's chi-square tests or Fisher's Exact tests. All analyses will be done using SAS (version 9.4, The SAS Institute, Cary, NC) and a p < 0.05 will be considered statistically significant.

Timetable:

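### The primary endpoint takes its baseline hemoglobin within 72 hours of surgery, after randomization and the presurgical intervention, so it subtracts any gain made by then

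*Combined protocol and SAP*

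**What the plan says.** Specific Aims/Objective defines the primary outcome as a change in hemoglobin, "defined as the difference of the hemoglobin level obtained within 72 hours prior to surgery and the hemoglobin level at 4 weeks postoperatively". Table 1.0 lists the earlier value as "Baseline Hemoglobin (pre-op" and the later one as the postoperative level. It has no field for the hemoglobin that qualified the patient.

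Methods and Study Design puts randomization earlier. Patients with a qualifying hemoglobin (11 g/dL or lower, within 30 days of the consultation) are eligible, and "they will be consented and randomized at the consultation visit". For those first seen at another site, the "follow up preoperative visit will be scheduled at the main campus where consent will be obtained". Patients are "randomly allocated to receive presurgical optimization blood management referral versus usual care". Background/Introduction says of the program: "Any correctable causes of anemia will be addressed preoperatively by the Blood Management group".

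Justification for Sample Size assumes that "patients at 4 weeks will have a standard deviation in hemoglobin values of 1.2 g/dL" and aims to detect 1 g/dL between groups, giving 24 per group and 60 enrolled after 20% dropout. Under Analysis plan, approximately normal continuous measures "will be compared using two-sample t-tests". No model adjusted for a baseline value is named.

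**The concern.** A baseline for a randomized comparison has to be fixed before treatment can affect it. Here the sequence is qualifying hemoglobin, randomization, presurgical blood management or usual care, the 72-hour draw, surgery, and the 4-week draw. The value used as the starting point therefore comes after the treatment period and is itself an outcome of treatment.

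The trial's stated goal is to evaluate preoperative blood management, whose direct target is a higher hemoglobin going into surgery. Subtracting the 72-hour value removes that gain from the primary result. The better the program works before surgery, the more is subtracted. Randomization keeps the comparison of change scores free of confounding, but the quantity compared is not the program's effect on 4-week hemoglobin. The trial could report no effect, or an effect in favour of usual care, for a program that raises hemoglobin at both times.

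A related mismatch is that the sample size uses the SD of 4-week values, whereas the endpoint is a change.

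**Working it through.** **Inputs from the documents.** Difference 1 g/dL; SD 1.2 g/dL for 4-week values; alpha 0.05; 80% power; t-test; 24 per group; 20% dropout (Justification for Sample Size). Sidedness is not stated; two-sided reproduces the plan's number.

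**Assumptions not in the documents.** The 1 g/dL is the true difference at 4 weeks (the plan ties only the SD to 4 weeks). SD is 1.2 at every reading. The correlation r between readings is 0.3, 0.5 or 0.7. G ranges from 0 to 1.5 g/dL.

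**1. The plan's own figure.** A two-sided t-test with difference 1 and SD 1.2 needs 23.6, so 24 per group, with 80.7% power. Then 48 / 0.8 = 60 enrolled. This reproduces exactly, for a comparison of 4-week values.

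**2. What the written endpoint estimates.** Take change as the 4-week value minus the 72-hour value; reversing the sign alters nothing below.
- Between-group difference at 72 hours: G
- Between-group difference at 4 weeks: D
- Between-group difference in change: D − G

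**3. SD of the change.** 1.2 × √(2(1 − r)) = 1.420, 1.200 and 0.930 at r = 0.3, 0.5 and 0.7.

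**4. Chance of a significant result on the written endpoint** (D = 1, 24 per group, noncentral t):

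| G (g/dL) | Expected contrast | Direction counted | r = 0.3 | r = 0.5 | r = 0.7 |
|---|---|---|---|---|---|
| 0 | 1.00 | blood management | 67% | 81% | 95% |
| 0.25 | 0.75 | blood management | 43% | 56% | 78% |
| 0.50 | 0.50 | blood management | 22% | 29% | 45% |
| 0.75 | 0.25 | blood management | 9% | 11% | 15% |
| 1.00 | 0 | blood management | 2.5% | 2.5% | 2.5% |
| 1.50 | −0.50 | usual care | 22% | 29% | 45% |

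**5. The SD mismatch on its own.** Suppose instead that the 1 g/dL is the difference in the change score itself. Power is then the first row of the table, and 80% power needs 33, 24 or 15 per group. Dividing by 0.8 and rounding up within each group gives 42, 30 or 19, that is 84, 60 or 38 enrolled. The planned 60 fits a change score if r is about 0.5 or higher.

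**6. Four-week hemoglobin as the outcome.** G does not enter this comparison.
- Unadjusted t-test: 80.7% power.
- ANCOVA on the pre-randomization value: residual SD = 1.2 × √(1 − r²) = 1.145, 1.039 and 0.857, with 45 degrees of freedom. Power is 84%, 90% and 98%. Here r is the correlation between the pre-randomization and 4-week values.

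**7. A simple change from the pre-randomization value.** This also removes the defect. With an entry SD of 1.2 and r = 0.3, power is 67%. Entry is capped at 11 g/dL, so the entry SD is probably smaller. With entry SD s, the SD of change is √(1.44 + s² − 2 × 0.3 × 1.2 × s). For s = 1.0, 0.8, 0.6 and 0.4 this is 1.311, 1.226, 1.170 and 1.145, giving power of 73%, 79%, 83% and 84%. ANCOVA gives 84% at r = 0.3 whatever s is.

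**The case against.** The strongest objection is that G is unknown and could be small. The program may consist of observation or oral iron, usual care may also include oral iron, and the interval from randomization to surgery is not stated. If G is zero, nothing is lost. This stands as a limit on the size of the problem, and the values G = 1.0 and 1.5 are illustrations only. It does not rescue the endpoint. A G near zero would mean that the presurgical program had not raised preoperative hemoglobin relative to usual care, and the alternative analysis is valid in that case too.

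A second objection is that the change from 72 hours before surgery to 4 weeks after describes perioperative fall and recovery, which is a coherent quantity. So it is, but it does not answer the stated aim of evaluating preoperative blood management, and the plan presents it as a change in baseline hemoglobin.

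Third, the case against a simple change from the pre-randomization value should not rest on the 67% figure, which assumes an entry SD of 1.2. This is right: with a narrower entry SD that analysis approaches ANCOVA. ANCOVA is still at least as powerful throughout, so it remains the better choice, though by a margin that may be small.

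Fourth, the SD mismatch is a separate matter and is harmless at r = 0.5. Agreed; it adds little to the seriousness of this point.

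The patient flow figure and the treatment algorithm are not readable here, but nothing in the readable text gives another reference value for the primary endpoint.

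**Conclusion.** The concern holds and should be corrected before the analysis. The reference hemoglobin is measured after randomization and after the presurgical treatment period, so the planned contrast is D − G rather than the effect on 4-week hemoglobin. That follows from the plan's own timing and needs no assumption.

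The size of the loss does depend on assumptions. With a true 4-week difference of 1 g/dL, SD 1.2 and 24 per group, a preoperative gain of 0.25 g/dL leaves power of 43% to 78% over correlations of 0.3 to 0.7, and a gain of 0.5 leaves 22% to 45%. A fully maintained gain (G = D) has an expected result of zero, and a partly lost one (G > D) points towards usual care. A larger sample does not cure the last two cases.

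**What to change.** - Make hemoglobin at 4 weeks after surgery the primary outcome. Compare groups by ANCOVA with the last hemoglobin before randomization (the qualifying value) as covariate.
- Name this model in Analysis plan, which now lists only t-tests, Wilcoxon, chi-square and Fisher tests.
- Restate the sample size for this outcome. The 48 evaluable and 60 enrolled can stand, provided the sponsor confirms that the 1 g/dL target is the difference at 4 weeks.
- Prefer ANCOVA to a simple change from the pre-randomization value as the primary analysis.
- Report the hemoglobin within 72 hours before surgery as a separate outcome, showing the direct preoperative effect. The change from that draw to 4 weeks can be kept as description.
- Add a field for the qualifying hemoglobin and its date to Table 1.0.
- Make the change, including the registration wording, before any outcome data are viewed by arm.

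The cost is revised wording and a small addition to data collection. The qualifying value is already obtained for eligibility and held in the medical record. No extra blood draw, patient or change in care is needed.

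### Clinical events between randomization and surgery, the period in which the two arms are treated differently, are not among the listed outcomes or data variables

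*Combined protocol and SAP*

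**What the plan says.** Methods and Study Design places randomization early. For a woman with a qualifying hemoglobin already on record, "they will be consented and randomized at the consultation visit". The arms then part. In the intervention arm, according to the Background, "Any correctable causes of anemia will be addressed preoperatively by the Blood Management group", with oral or intravenous iron among the possible measures. Under usual care, management "may include no treatment, continued observation, or oral iron recommendations in the pre-operative time".

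Specific Aims/Objective defines the primary endpoint as "the difference of the hemoglobin level obtained within 72 hours prior to surgery and the hemoglobin level at 4 weeks postoperatively". The clinical secondary objective begins "To evaluate the perioperative outcomes between the two groups including OR times, EBL, peri-operative transfusion rates, length of hospital stay" and continues with "complications including intra-operative injuries, postoperative infection rates, readmission, and re-operation". Table 1.0 repeats the last group as "Intraoperative Complications o Intraoperative injuries o Post-operative infection rates Readmission Reoperation". Its items that do extend over the wait are "Number of infusions received • Days on PO iron therapy". A separate sentence plans to cost iron and transfusion and mentions health care utilization.

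Two other statements bear on the wait. The exclusion criteria rule out women transfused in the 30 days before surgery, a window counted back from the operation and not from randomization. Risks and Discomfort of the Project names a reaction to intravenous iron as the one physical risk.

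**The concern.** A randomized comparison of clinical outcomes should begin when the arms begin to differ. Here they differ from randomization until the operation, but the listed clinical events are tied to the operation and what follows. The possible harms of either strategy during the wait have no listed place: bleeding or symptomatic anemia leading to an emergency visit or admission, a reaction to an infusion, or an operation moved or not done.

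The transfusion exclusion adds a risk of bias. At the consultation visit nobody can know whether a woman will be transfused in the last 30 days before an operation that lies ahead. Any part of that window that falls after randomization can only be applied after randomization. A woman transfused for bleeding while waiting could then be excluded when she should be counted as an event. If that happens more often in one arm, the operative comparisons no longer rest on the groups that were randomized. The report could state that complications did not differ when the arms had in fact differed during the wait.

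**Working it through.** **The plan's own figure.** Justification for Sample Size gives SD 1.2 g/dL, difference 1 g/dL, 80% power and significance level 0.05.
- Normal approximation: 2 × (1.96 + 0.84)² × 1.2² / 1² = 22.6, so 23 per group.
- Two-sided t-test: 23.6, so 24 per group and 48 in total, as stated.
- Dropout: 48 / 0.80 = 60, as stated.

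The sample size reproduces and is not in dispute.

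**Each listed item set against the time of randomization.**

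| Item | Source | Reaches into the wait? |
|---|---|---|
| Hemoglobin change | Specific Aims | Only its first value, at most 72 hours before surgery |
| OR time, blood loss, length of stay | Specific Aims, Table 1.0 | No |
| Injuries, postoperative infection, readmission, re-operation | Specific Aims, Table 1.0 | No |
| Peri-operative transfusion | Specific Aims, Table 1.0 | Unclear; no window given |
| Number of infusions, days on oral iron | Table 1.0 | Yes, as exposure |
| Cost of iron and transfusion | Text after Table 1.0 | Partly, as treatment cost |
| Unplanned visit or admission before surgery | Not listed | – |
| Reaction to intravenous iron | Named as a risk, not listed as a variable | – |
| Surgery expedited, postponed or not done | Not listed | – |
| Randomization date | Not listed | – |

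**Effect of the exclusion (illustration).** Suppose one of 30 control women is transfused during the wait. Counted, she contributes 1/30 = 3.3%. Excluded after randomization, the arm shows 0/29 = 0%.

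**Scale.** The documents give neither the length of the wait nor an event rate in it. With an assumed control rate of 5–15%, 0.05 × 30 = 1.5 and 0.15 × 30 = 4.5 women. For orientation only, the 13.3% transfusion rate cited in the Background gives 0.133 × 30 = 4.0. That is an overall hysterectomy rate from one study, not a rate for this anemic population.

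**What 30 per arm can show.** All rates below are assumed. Power is for Fisher's exact test at 0.05; n per arm for 80% power uses the pooled normal formula.

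| Control vs intervention | Expected events | Power at 30 per arm | n per arm for 80% |
|---|---|---|---|
| 5% vs 2% | 1.5 vs 0.6 | 0.2% | 588 |
| 10% vs 3% | 3.0 vs 0.9 | 3% | 194 |
| 15% vs 5% | 4.5 vs 1.5 | 9% | 141 |
| 20% vs 5% | 6.0 vs 1.5 | 24% | 76 |
| 30% vs 10% | 9.0 vs 3.0 | 37% | 62 |

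Even no events in 30 women leaves an exact 95% upper limit of 1 − 0.025^(1/30) = 11.6%. These events can be described with confidence intervals but not usefully tested.

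**The case against.** The strongest reply is that this is a choice of scope. The stated goal concerns surgical outcomes and the morbidity linked to postoperative transfusion, and perioperative outcomes suit that goal. Care before surgery would be a further question, and with 30 per arm the added data would hardly change a finding of no difference. The point about power stands. The scope argument stands only in part, because the plan also wants to judge blood management on health care utilization and names a harm that would occur at a preoperative infusion.

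Several stronger readings are tempting, and the documents do not support them.
- A reader might infer that nothing in the wait is recorded. That goes too far: preoperative hemoglobin, infusions, days on oral iron and perhaps some transfusions reach into it.
- A reader might infer that a control woman who bleeds cannot be told apart from one who does not. She may show a lower preoperative hemoglobin, and applying the exclusion requires someone to find out about a transfusion.
- A reader might infer that a woman whose surgery is cancelled vanishes entirely. She would lack the surgery-anchored hemoglobin values and the operative outcomes, but exposure data and an early RAND-36 could still exist.
- A reader might infer that arranging infusions delays surgery. No document says so, and the Background says treatment plans take upcoming procedures into account.

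Table 1.0 is also not shown to be exhaustive. It omits the assigned arm and the stratifying provider, which the trial must hold, and the patient flow sheet is a figure that is not shown. The randomization date may therefore exist elsewhere. It cannot simply be assumed to equal the first consultation, because women first seen at the two other hospitals give consent at a later visit on the main campus.

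**Conclusion.** The point holds in a limited form. The arms are treated differently from randomization to surgery, while the listed clinical outcomes concern the operation and its aftermath. Unplanned care, infusion reactions and changes to the operation during the wait are not listed. The transfusion exclusion, if applied after randomization, would remove women on the basis of an event that allocation may influence; the documents do not say when it is applied, and the Analysis plan states no analysis set.

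All 60 planned women pass through this period. The number affected is unknown: 1.5 to 4.5 of 30 controls rests entirely on the assumed 5–15%. The weakness lies in freedom from bias and in safety reporting. It is not an error in the sample size, and the definition of the primary endpoint is unaffected. The change is worth making before enrollment because reasons for moved operations and care at outside hospitals may be hard to recover later.

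**What to change.** Start clinical-event collection at randomization. Add to Table 1.0:
- the randomization date;
- any unplanned emergency visit, admission or transfusion before surgery;
- any infusion reaction;
- surgery expedited, postponed or not done, with the reason.

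Take these from EPIC, plus one question at the postoperative visit. In the Analysis plan, state that they will be reported descriptively by assigned arm, as counts with confidence intervals, with all randomized women as the denominator. State also that, in defining the analysis set, the transfusion exclusion applies only to transfusions before randomization; a later one is counted as an event. This concerns analysis and changes nothing in any woman's care.

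The cost is a few REDCap fields and some chart review, with no extra visit or test. The remaining weakness is that events at outside hospitals depend on recall.
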